4 STUDY DESIGN

4.1 Overall Design

This is a Phase IIB, randomized, double-blinded, placebo-controlled, parallel-group study to evaluate the efficacy, safety, PK, and immunogenicity of MEDI6570 in participants 30 to 365 days post-MI with persistent inflammation defined as hs-CRP \geq 1 mg/L. Participants will be randomized to receive CCI mg (in an injection volume of 1.5 mL), or CCI mg (in an

injection volume of 4.0 mL) MEDI6570, or injection/volume-matched placebo (1.5 or 4.0 mL), subcutaneously (SC), every 4 weeks (Q4W) for 32 weeks (9 doses in total). Approximately 400 participants will be randomly assigned to a study intervention, with an anticipated 369 participants being randomized to receive active study intervention (123 participants in each of the 2 MEDI6570 groups), and 123 participants being randomized across the 3 placebo groups (ie, including participants already randomized to the legacy dose/volume-matched placebo group for the [CC1] mg dose). It is estimated that approximately 360 evaluable participants (111 evaluable participants in each of the 2 MEDI6570 groups [CC1 and CC1 mg], plus 27 evaluable participants in the legacy [CC1] mg MEDI6570 group, plus 111 participants across the 3 placebo groups) will complete the study. The randomization will be stratified by geographic region (Asia, North America and Rest of World) and by statin therapy status (no, low- or moderate-intensity statin therapy vs high-intensity statin therapy; refer to [Appendix F](#)) at baseline.

Participants who were randomized to a study intervention under Protocol Version 1.0 or Amendment 1 (when there was also a [CC1] mg dose group) and were allocated a dosing volume of 0.5 mL will continue on their randomized study intervention ([CC1] mg MEDI6570, or its injection/volume-matched placebo) to the end of the study, and the study blind will be maintained with regard to active versus placebo.

In accordance with the ESC/EAS and ACC/AHA guidelines regarding lipid modification and the reduction of residual CV risk, the use of high-dose statins in secondary prevention is a Class I recommendation with Level A evidence to support it ([Mach et al 2020](#), [Grundy et al 2019](#)). As such, and in keeping with the expected standard of care, the implementation and maintenance of the highest tolerated dose of statins (although not mandated) is strongly encouraged in this study population.

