^a Under Protocol Amendment 2, no new participants will be randomized to the [REDACTED] mg dose group or its injection/volumed matched placebo (0.5 mL); participants who were randomized to [REDACTED] mg MEDI6570 or its injection/volume-matched placebo will continue on their randomized intervention until the end of the study. For participants enrolled under Amendment 2, there will be 2 placebo groups to match the dosing volumes of the 2 active groups: 1.5 and 4.0 mL.

IMP, investigational medicinal product; NA, not applicable; NIMP, non-investigational medicinal product; Q4W, every 4 weeks; SC, subcutaneous; w/v, weight per volume.

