6.3.2 Blinding Procedure

The participant, the investigator, and the site staff performing study-related procedures will all be blinded to the participant's intervention group, with respect to active treatment versus placebo, to minimize bias.

The RTSM will provide to the investigators or pharmacists the kit identification number to be allocated to the participant at the dispensing visit. Routines for this will be described in the RTSM user manual provided to each study site.

The sponsor retains the right to break the code for SAEs that are unexpected and are suspected to be causally related to the study intervention and that potentially require expedited reporting to regulatory authorities. Randomization codes will not be broken for the planned analyses of data until all decisions on the evaluability of the data from each individual participant have been made and documented.

The RTSM will be programmed with blind-breaking instructions. In case of an emergency, in which the knowledge of the specific blinded study treatment will affect the immediate management of the participant's condition, the investigator has the sole responsibility for determining whether unblinding of a participant's intervention assignment is warranted. Participant safety must always be the first consideration in making such a determination. If a participant's intervention assignment is unblinded, the sponsor must be notified within 24 hours after breaking the blind. The investigator must document and report the action to the sponsor, without revealing the participant's treatment to the sponsor's staff.

Participants enrolled under Protocol Amendment 2 will be randomly assigned to one of 4 possible intervention groups in a 2:2:1:1 ratio: [REDACTED] mg (with an injection volume of 1.5 mL) or [REDACTED] mg (with an injection volume of 4.0 mL) MEDI6570, or an injection/volume-matched placebo (1.5 or 4.0 mL). Investigators will remain blinded to each participant's assigned study intervention, with respect to active treatment versus placebo, throughout the course of the study.

Participants who were randomized to a study intervention under Protocol Version 1.0 or Amendment 1 and were allocated a dosing volume of 0.5 mL will continue on their randomized study intervention (█ mg MEDI6570, or its injection/volume-matched placebo) to the end of the study, and the study blind will be maintained with regard to active versus placebo.

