9.2 Sample Size Determination

The 3 injection/volume-matched placebo groups will be pooled for the analyses.

CCI

CCI

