The dosing volumes and numbers of injections to be administered for each	The dosing volumes were reduced to minimize the number of injections	Section 6.1 Study Interventions Administered;

Description of Change	Brief Rationale	Sections Affected

intervention were changed, from 3 injections (totalling 2.5 mL, for all interventions), to 1 injection (of 0.5 mL for the CC1 mg group and 1.5 mL for the CC1 mg group) or 2 injections (totalling 4 mL for the CC1 mg group).
 
Consequential changes are outlined below:
 
 The placebo intervention now comprises 3 injection/volume-matched placebo groups, and the randomization ratio has changed (from 1:1:1:1 for 3 MEDI6570 dose groups and 1 placebo group to 3:3:3:1:1 for 3 MEDI6570 dose groups and 3 injection/volume-matched placebo groups. Text was amended to clarify that the study is blinded with respect to active treatment versus placebo. Text was added to explain that participants enrolled under Protocol Version 1.0 will be re-allocated to the appropriate dosing volume for their randomized intervention group, and that participants originally randomized to receive placebo will be re-randomized to a placebo group that is injection/volume-matched to a MEDI6570 treatment group. Text was added to explain that the 3 injection/volume-matched placebo groups would be pooled for the analyses. 	
required and to make the study more patient-centric.
 
 To maintain the study blind between active treatment and placebo In minimizing the numbers of injections required at each dose level to make the study more patient-centric, is no longer blinded with regard to dose level, but it remains blinded to active versus placebo. To transition participants from Protocol Version 1.0 to Amendment 1 while maintaining the integrity of the randomization schedule and the study blind (with regard to active versus placebo) For clarification 	
Section 1.1 Synopsis; Section 6.2.3 Dose Preparation Steps, text and Table 9; Section 6.2.4 Treatment Administration
 
• Terms and Conventions Used in this Document; Section 4.1 Overall Design; Section 4.3 Justification for Dose; Section 6.2.3 Dose Preparation Steps, text and Table 9; Section 6.2.4 Treatment Administration; Section 6.3.1 Randomization Procedure; Section 6.3.2 Blinding Procedure
 
• Section 6.3.2 Blinding Procedure
 
• Section 6.3.1 Randomization Procedure; Section 6.3.2 Blinding Procedure
 
• Section 1.1 Synopsis; Section 9.2 Sample Size Determination

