4 ANALYSIS METHODS

4.1 General principles

Data will be summarized using descriptive statistics at each visit. For the analyses and listings, placebo will be the 3 injection/volume-matched placebo groups pooled. Treatment groups will be:

- MEDI6570 with dose **CCI** and placebo for ITT, CTA analysis, Echocardiogram analysis populations. In these analyses, subjects initially randomized to the **CCI** group who consented to CSP amendment 1 and were switched to **CCI** dose were analysed according to the **CCI** group. For the safety and efficacy analyses, the number of subjects randomized to the **CCI** group who consented to amendment 1 of the CSP and switched to the **CCI** dose is specified.
- MEDI6570 with dose **CCI** or **CCI** and placebo for as treated, Per-protocol CTA analysis and Immunogenicity populations. In these analyses patients treated within **CCI** group who received at least one **CCI** dose during the study will be analysed according to the **CCI** group.
- MEDI6570 with dose **CCI** or **CCI** and **CCI** (listing only) and placebo for PK and **CCI** analysis populations. Subjects who only received **CCI** will be analysed according to the **CCI** group. Subjects who received both **CCI** and **CCI** doses during the study will be analyses as a separate **CCI** group. Due to few subjects in **CCI** treatment group they will not be included in summary table and figures as well as in modelling outputs. They will be included in listings only.

For continuous variables and unless otherwise specified descriptive statistics will include the number of subjects (n), mean, SD, median, minimum, and maximum. The 1st and 3rd quartiles will be added to exposure and ADA only if not requested otherwise. If the parameter is assumed to be log-normally distributed, the descriptive statistics will additionally include geometric mean (GeoMean) and geometric coefficient of variation (GeoCV). For geometric mean calculation, variables records with zero value will be imputed by half of the minimum of the non-zero records prior to the log-transformation.

Decimal places will always apply the following rules:

- n will be presented as integer.

- Percentage (including CV and GeoCV) will be presented with 1DP except Kaplan Meier (KM) estimate that will be with 2DP.
- For derived variables, the precision of the calculated variable will be one more than the least number of decimal places among the raw data used for calculation with a maximum of 3DP.

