4.2.10.7 Adverse events

After having assigned the AEs to the corresponding analysis phase as described in section [3.3.5.1](#), the AEs will be summarized for each treatment group and overall (total will not include placebo subjects). The AEs tables will be based on the as-treated population except the AE by ADA tables which will be based on the Immunogenicity population. Summary tables will include AEs in the on-treatment phase and AEs in the follow-up phase.

Summary tables are listed below.

An overview table containing:

- Number and percentage of subjects with any AEs
- Number and percentage of subjects with any AEs with outcome of death
- Number and percentage of subjects with any SAE (including events with outcome = death)
- Number and percentage of subjects with any AEs leading to discontinuation of treatment
- Number and percentage of subjects with any AEs leading to withdrawal from study

Subjects with multiple events in the same category are counted only once in that category.
Subjects with events in more than 1 category are counted once in each of those categories.

An overview table containing:

- Any AE
- Any AEs with outcome of death
- Any SAE (including events with outcome of death)
- Any AE leading to discontinuation of treatment
- Any AE leading to withdrawal from study

Multiple events in the same category are counted multiple times in that category. Multiple events belonging to more than 1 category are counted multiple times in each of those categories.

The following summary tables will be presented by SOC and PT:

- The number and percentage of subjects with any AEs
- The number of AEs
- The number and percentage of subjects with AEs with outcome of death
- The number of SAEs
- The number and percentage of subjects with SAEs
- The number and percentage of subjects with SAEs, assessed by investigator as possibly related to investigational product
- The number and percentage of subjects with AEs leading to discontinuation
- The number and percentage of subjects with any bleedings (all events from bleeding event form or from adverse event form with SMQ= “Haemorrhages narrow”)
- The number and percentage of subjects with any injection site reactions (all events from ISR form or from adverse event form with HLT= “Injection site reactions”)
- Overall summary of number and percentage of subjects with any AEs by ADA (anti-drug antibody category)
- The number and percentage of subjects by ADA (anti-drug antibody category)

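### The injection-site-reaction table sets each active dose beside one pooled placebo column, although injection volume and number of injections differ by dose and each dose has its own volume-matched placebo

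*SAP*

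**What the plan says.** SAP 4.1 sets the rule for analyses and listings alike: "placebo will be the 3 injection/volume-matched placebo groups pooled". Protocol 9.2 agrees: "The 3 injection/volume-matched placebo groups will be pooled for the analyses". Neither makes an exception for safety.

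The groups being pooled differ in what was injected. For participants enrolled under Amendment 2, protocol 6.1 (Table 8, footnote a) says "there will be 2 placebo groups to match the dosing volumes of the 2 active groups: 1.5 and 4.0 mL". Protocol 6.3.2 adds the legacy group: earlier participants who "were allocated a dosing volume of 0.5 mL will continue on their randomized study intervention". On number of injections, the Amendment 1 history (protocol Appendix I) gives one at 0.5 mL and one at 1.5 mL, "or 2 injections (totalling 4 mL for the" highest-volume group. The current dose-preparation table is redacted, but protocol 6.2.3 has doses drawn into syringes of at most 3 mL, so 4.0 mL needs at least two.

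SAP 4.2.10.7 plans, by SOC and PT and for each treatment group, "The number and percentage of subjects with any injection site reactions". No output divides placebo by volume or number of injections. The adverse-event outputs go into the IDMC reports as well as the final analysis.

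**The concern.** Injection-site reactions are a named risk (protocol Table 6) and are assessed at every dosing visit. The safety objective is a comparison with placebo. For this event, unlike plaque volume, the volume injected and the number of needle insertions could plausibly matter whatever the syringe contains. Each active group has a single volume, while its comparator column is a mixture of three. No dose column is therefore read against placebo given in the same way.

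If reactions rise with volume or number of injections, an inert drug could look worse than placebo at 4.0 mL and better at 0.5 and 1.5 mL. In a dose-range-finding study that could pass for a dose trend in local tolerability. It could also colour the DMC's review of the increased dose, which protocol Appendix A 5 assigns to it. The blind covers active versus placebo, not volume, so the volume-matched contrast is also the one in which participants had the same visible experience.

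**Working it through.** **Group sizes.** The plan's evaluable total reproduces: 2 x 111 + 27 + 111 = 360. Against about 400 randomized, implied dropout is 1 - 360/400 = 10%. The legacy active group is then about 27/0.9 = 30 randomized, and 3 x 123 + 30 = 399, in line with 400. (The protocol's 369 on active treatment equals 3 x 123 and seems to include placebo, since 369 + 123 = 492. This does not affect the point.)

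**Placebo split (estimate).** The documents do not give it. The Amendment 1 log prints five numbers (3:3:3:1:1) for six groups; I assume 3:3:3:1:1:1. Legacy placebo is then about 30/3 = 10. The other 113 of 123 divide equally between 1.5 and 4.0 mL, 56.5 each. The mix is 8% / 46% / 46% at 0.5 / 1.5 / 4.0 mL.

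**Apparent difference with no drug effect.** With rate p1 for one injection and p2 for two:

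pooled rate = (66.5 x p1 + 56.5 x p2)/123

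Each active group's apparent difference is its own rate minus the pooled rate. All rates are assumptions.

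| One injection | Two injections | Pooled placebo | 4.0 mL (points) | 1.5 mL (points) |
|---|---|---|---|---|
| 5% | 5% | 5.0% | 0 | 0 |
| 2% | 3.96% = 1 - 0.98^2 | 2.9% | +1.1 | -0.9 |
| 2% | 6% | 3.8% | +2.2 | -1.8 |
| 5% | 9.75% = 1 - 0.95^2 | 7.2% | +2.6 | -2.2 |
| 5% | 15% | 9.6% | +5.4 | -4.6 |

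Rows two and four treat two injections as two independent chances of a reaction. Rows three and five assume a tripled rate. In all rows 0.5 mL behaves like 1.5 mL, because only the number of injections varies.

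If volume itself matters, with assumed rates of 2% / 5% / 10% at 0.5 / 1.5 / 4.0 mL, the pooled rate is (10 x 2 + 56.5 x 5 + 56.5 x 10)/123 = 7.05%. The differences are then -5.1, -2.1 and +2.9 points. Against volume-matched placebo the expected difference is zero in every scenario.

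**Precision.** For 4.0 mL (123 active), total error (root of squared bias plus sampling variance) against pooled placebo (123) and matched placebo (56.5):

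- 2% / 6%: pooled sqrt(0.06 x 0.94/123 + 0.0384 x 0.9616/123 + 0.0216^2) = 3.5 points; matched sqrt(0.06 x 0.94/123 + 0.06 x 0.94/56.5) = 3.8 points.
- 5% / 9.75%: 4.4 pooled, 4.8 matched.
- 5% / 15%: 6.8 pooled, 5.7 matched.

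**All-active total.** Its mix is about 30/276 = 11%, 123/276 = 45% and 45%, close to the placebo mix. The problem lies in the dose-specific columns.

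**The case against.** The output is counts and percentages. SAP 4.1 has a general rule for hypothesis tests, but no model or test is assigned to injection-site reactions, and no decision rule uses their rates. A reader might infer an inflated false-positive rate for a safety test; the documents plan no such test. A reader might also infer that the 4.0 mL group will look worse than placebo. That is not supported either: no reaction rates by volume or number of injections are given, and the apparent difference may be zero. Both points stand, and they limit the claim to what a side-by-side reading could suggest.

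Pooling also has a statistical case. For 4.0 mL the pooled column has the smaller total error in two of the three scenarios above, and a 0.5 mL placebo column of about 10 says almost nothing. This stands against replacing the pooled column. It does not stand against adding to it.

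Matching is imperfect. By the amendment history, Version 1.0 participants first had three injections totalling 2.5 mL in every arm. Under protocol 6.3.1 the placebo participants among them who had not completed treatment were re-randomized to a volume. Some of their reactions may belong to no matched volume, and the fix has to allow for this.

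Finally, randomization codes, kits, administration and all adverse events are listed, and the DMC can merge treatment codes with study data. Volume can therefore be recovered. But no such summary is planned, and one first made after unblinding would be post hoc.

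**Conclusion.** The point holds as a modest one about presentation. As planned, each dose column in the injection-site-reaction table is read against a placebo mixture of about 8% / 46% / 46% that does not match its own volume or number of injections. If these affect reactions, the drug's effect could be overstated at 4.0 mL and understated at 0.5 and 1.5 mL.

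Under the assumed one- and two-injection rates, the distortion at 4.0 mL runs from zero to about 5 percentage points, with one nearly as large in the other direction at 1.5 mL. This rests on assumed reaction rates, the estimated placebo split, and an injection count taken from the amendment history and supported by the syringe sizes. The pooling of placebo for imaging, biomarkers and other adverse events is not in question.

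**What to change.** In the injection-site-reaction table of SAP 4.2.10.7, for both the IDMC and final reports, show placebo split by volume with each active dose next to its volume-matched placebo, and keep the pooled placebo column. Count separately, or footnote, reactions that Version 1.0 participants had before re-allocation to a volume. Leave pooling for efficacy and other adverse events unchanged.

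The cost is a few columns in one descriptive table and a sentence of exception in SAP 4.1; no new data are needed. The volume-specific placebo columns are smaller and less precise: about 57 each at 1.5 and 4.0 mL, and about 10 at 0.5 mL, which is of little use alone.

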4.1.1 Analysis of covariance (ANCOVA)

The ANCOVA model will be used to fit change from baseline at each concerning visit. Data used in the model are data from baseline and the scheduled tested visit. The group of treatment will be considered as a fixed effect of the model while the baseline value and the stratification factors (geographic region and statin therapy intensity at screening) as covariates. Comparisons of MEDI6570 CCI versus placebo, MEDI6570 CCI versus placebo, MEDI6570 CCI versus placebo and pooled MEDI6570 CCI versus placebo will be assessed using the same model. The restricted maximum likelihood (REML) approach will be used for the estimation of the variance and covariance parameters of the linear mixed model; one sided difference test with alpha level at 5% and two-sided 90% CI will be used for the comparisons. No data imputation will be used.

In case of singularity between the covariates (i.e. within each treatment group subjects have exactly the same combination of both stratification factors), the second stratification factor (level of statin therapy) will be removed from the model.

ANCOVA model will be run by subgroup see section [4.2.8.1.5](#), [4.2.8.2.2](#), [4.2.8.3.2](#), [4.2.10.1.1](#) for details. In case of low number of subjects (less than 13 observations) in a subgroup the results will not be provided since there are not estimable or not reliable.

If the parameter is assumed to be normally distributed, the variable fitted in the model will be the change from baseline; the ANCOVA model and the reportable results will be those described below:

- The least-square means (LSmeans) and their standard errors for each group

- The difference between active groups and placebo (LSmean difference) together with its 90% CI
- The one-sided p-value for the difference between active groups and placebo

If the parameter is assumed to be log-normally distributed, the variable fitted in the model will be the change from baseline in logarithmical scale. Change from baseline in logarithmical scale is defined as the log-transformation of the post-baseline visit value minus the log-transformation of the baseline value.

The ANCOVA model will be as described above but the reportable results from the model will be:

- Back transformed LSmeans for each group using exponential (EXP) function, calculated as: EXP (LSmeans of the logarithmic transformation) = Geometric LSMeans and their back transformed Coefficient Variance $\{ \text{SQRT} [(\text{EXP} (\text{variance for log transformed data})) - 1] \} * 100 = \text{SQRT} [(\text{EXP} ((\text{SD}) - 1))] * 100$,
- The ratio between active groups and placebo; the ratio is calculated as EXP (LSMean difference) together with its back-transformed 90% CI, calculated as [EXP(Lower)]; [EXP(Upper)].
- the one-sided p-value of the comparison between active groups and placebo

To be noted that a ratio lower than 1 means that the active group shows a higher decrease (or a lower increase) compared to the placebo group. On the other hand, a ratio greater than 1 means that the active group shows a lower decrease (or a higher increase) compared to the placebo group.

The ANCOVA model will be used at final analysis.

